1.2 What is the principal research question to be addressed?

In toddlers (aged 18–42 months) with confirmed or suspected autism, is virtual, Group-based intervention using the *Social ABCs* model, more effective than treatment as usual at increasing toddlers' vocal responsiveness to their primary caregivers (i.e., parents)?

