2.5 What are the planned inclusion/exclusion criteria?

Inclusion Criteria. Eligibility will be based on elevated scores on the Autism Parent Screen for Infants (APSI³⁷) supported by expert clinician impression of red flags for autism spectrum disorder (ASD), or a confirmed diagnosis of ASD made by a qualified professional (parents will be asked to provide the clinical report). Toddlers will be between ages 12 and 42 months at enrollment, having been born between 36 and 42 weeks’ gestation, with birthweight $>2,500$ g and no neurological, genetic, or severe sensory or motor conditions. Participating families must be residing in Ontario, Nova Scotia, or Alberta at the time of participation.

Requirements for participation include ability to comprehend verbal English instructions. Our Parent Training Manual is written at a grade four language level, but concepts are shared verbally and through images, so literacy is not a requirement. Participation is also dependent on access to high-speed internet and willingness to be video-recorded, for cross-site consistency checks and data acquisition. Parents will be asked to limit other social communication intervention programs (e.g., through Speech-Language Pathology, Occupational Therapy, Applied Behaviour Analysis, or related services) to 1 hour per week. Parents will also complete weekly services log to document involvement in such programs. Finally, parents will be encouraged to try not to miss more than 2 sessions in a row. Missed sessions will be rescheduled if possible. However, all families will be invited to provide end-of-study data even if multiple sessions are missed (number of sessions attended will be used as a covariate in analyses). Families may withdraw at any time.

There are no ***exclusion criteria*** other than failure to meet inclusion criteria.

2.6 Proposed duration of treatment period.

Treatment duration is 6 weeks. Time span between data collection time points will range from 7 to 9 weeks to allow for re-scheduling if necessary.

2.7 Proposed frequency and duration of follow up.

Data will be collected for both groups at: baseline (*Time 0*), 6 weeks later (*Time 1; within 6-8 weeks*), and following the next 6 weeks (*Time 2; within next 6-8 weeks*). Time 2 for the treatment group provides follow-up data to examine maintenance of gains in our primary outcome (toddler vocal responsiveness) and parent fidelity.

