2.9 How will the outcome measures be measured at follow up?

Primary Outcome: Toddler vocal responsiveness. Consistent with our previous work^{21,22}, video coding will be used to measure toddlers' vocal responsiveness (proportion of appropriate child vocal responses following a caregiver prompt, from 10-minute video). All video coding will be conducted by blinded research staff with established reliability, per established protocols. *The primary outcome is change in toddler vocal responsiveness from time 0 to time 1.*

***For all parent-child interaction videos**, parents are instructed to: “*play with your child as you typically play*” and reminded that: “*we want to see both of you on the screen as much as possible*”. **Two 10-minute video clips** will be collected and coded per time point (using average per time-point for analyses); **no coaching occurs during data videos**. Videos will be collected by research staff over the virtual platform, saved to virtual drives within institutional firewalls, and shared securely for coding, based on formal data-sharing agreements. **Blinded research staff with established inter-rater reliability will code all videos, per established protocols.**

Secondary Outcomes (all measures used in our previous and/or ongoing work):

1. *Toddlers.* (a) Vocal initiations and (b) social orienting (both blind-coded from video); (c) parent-rated word inventory (MacArthur-Bates Communicative Development Inventory [CDI]³⁸); (d) autism symptoms (APSI³⁷). 2. *Parents.* (a) Correct use of *Social ABCs* strategies (%)

implementation fidelity from blind-coded video), (b) self-efficacy (Parent Self-Efficacy Scale²² developed for our previous work), (c) parenting stress (Parenting Stress Index-4-Short Form³⁹).

Exploratory Analyses:

1. **Predictor variables:** Continuous (parenting stress, child age, baseline word inventory, ASD symptoms) and categorical (toddler sex, parent gender, parenting role, educational attainment, employment, ethnicity, English spoken at home, family structure), variables (collected from the *Family Profile Form*²⁴) will be assessed for their effect on the outcomes;

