2.16 What is the proposed type of analyses?

The primary analysis will yield a comparison of rates of toddler vocal responsiveness between the two conditions, controlling for the variables described above. The statistical model for the

Primary Outcome will be either a Poisson or negative binomial regression (if there is overdispersion of the counts), using the number of prompts and/or time as offsets and applying the appropriate correlation structure for observations by participant, and controlling for intraclass correlation due to clustering. Growth curve analysis will be used to calculate the trajectory of change in responsive vocalizations over time for each person based on whatever data are available (if at least 2 measurements), and then estimates (imputes) the missing data if the person followed the same trajectory. Otherwise, a worst-case (no vocal response) scenario can be used.

Secondary Outcomes: We will analyze as per the primary outcome for count variables (e.g., video-coded toddler initiations). We will use repeated measures ANOVA or Generalized Estimating Equations for scores (e.g., word inventory, ASD symptoms, parent efficacy, stress).

Exploratory Analyses: (1) *Predictors* of primary and secondary outcomes will first be assessed univariately for their effect on the outcomes, and significant factors will be subjected to multivariate analysis using the appropriate regression model. We will examine the influence of sex (toddlers), parent gender, and parenting roles by entering these factors as covariates. Given that sample size calculations are not done for all these factors, these analyses are exploratory. (2) *Implementation metrics* (feasibility, acceptability) will be examined descriptively.

[figure not shown]
2.17 Proposed frequency of analyses. Analyses will be conducted at two time points: (1) following the end of Phase 1 ($n = 30$), and (2) at the end of the larger trial ($n = 100$).

2.18 Planned subgroup analyses.

Subgroup analyses, run separately for treatment and control groups, will explore effects of: (1) sex: *Do outcomes differ for boy vs. girl toddlers?*; (2) gender: *Are there differences in parent fidelity and self-efficacy based on self-identified parent gender?*; (3) baseline language functioning: *Do outcomes differ for toddlers who begin the program below (vs. at or above) a 12-month language level (based on parent-reported CDI scores)?*

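### The baseline-language subgroup uses one 12-month cut for all ages without age adjustment, so it mixes age with delay and loses information from a continuous score

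*Protocol*

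**What the plan says.** Section 2.18 lists three subgroup questions, each examined within the treatment arm and within the control arm. The third divides toddlers by baseline language into those "below (vs. at or above) a 12-month language level", "based on parent-reported CDI scores". It mentions no age adjustment and no age-relative score, and gives no reason for the cut.

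On age, section 2.5 states "Toddlers will be between ages 12 and 42 months at enrollment". The research question in section 1.2 gives a narrower range: "In toddlers (aged 18–42 months) with confirmed or suspected autism".

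The protocol also treats the same measure in another way. The exploratory part of section 2.9 names the predictors as "Continuous (parenting stress, child age, baseline word inventory, ASD symptoms) and categorical" variables, so baseline word inventory and child age are both kept continuous there. Section 2.9 further lists baseline language level among the child factors for subgroup and predictor work, without fixing its form. Under section 2.16, predictors are first tested one at a time; then "significant factors will be subjected to multivariate analysis using the appropriate regression model". That section says of the predictor work that "these analyses are exploratory".

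**The concern.** There are two problems with the comparison as fixed in section 2.18.

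First, a single absolute language level means different things at different ages. A toddler of about one year just below the cut is close to age level, while a child of three and a half just below it is far behind. Both go into the same subgroup. If language grows with age, younger children will also be over-represented below the cut. A difference between the two groups could then reflect age, delay or both, and the stated analysis cannot separate them.

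Second, cutting a continuous score in two treats children just either side of the threshold as different and children far apart on the same side as alike. Each comparison is made within one arm of about 50, where precision is already low.

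At stake is the reading of a secondary question: whether language at entry is related to outcome. An age effect could be reported as a language effect, or a real language relation could be missed.

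**Working it through.** The protocol gives no figure on this point, so there is nothing of its own to reproduce.

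**Inputs from the protocol**
- Cut: a 12-month language level on the CDI (2.18).
- Age range: 12 to 42 months (2.5), or 18 to 42 months (1.2).
- Comparisons made within each arm (2.18), with about 50 children per arm (2.10).

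**Not in the protocol:** the distribution of baseline CDI scores, the share of children below the cut, and the shape of the relation with outcome. Steps 2 to 4 therefore rest on assumptions.

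**Step 1. Age and delay.** The cut as a share of age is 12 / age in months, and the gap is age − 12.

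| Age (months) | 12 / age | Gap (months) |
|---|---|---|
| 12 | 100% | 0 |
| 18 | 67% | 6 |
| 24 | 50% | 12 |
| 30 | 40% | 18 |
| 42 | 29% | 30 |

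Under the 12-42 range, children just below the cut run from about age level to about 30 months behind. Under the 18-42 range the spread is smaller but still runs from 67% to 29% of age. This step needs no distributional assumption.

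**Step 2. Information kept by the split.** For a normal score linearly related to outcome, with share p below the cut, the fraction kept is φ(z_p)² / [p(1 − p)]. Here z_p is the normal quantile at p and φ the normal density.
- p = 0.5: 0.3989² / 0.25 = 0.637, so 36.3% is lost.
- p = 0.3: 0.3477² / 0.21 = 0.576, so 42.4% is lost.
- p = 0.2: 0.2800² / 0.16 = 0.490, so 51.0% is lost.

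The formula is symmetric, so p = 0.7 and p = 0.8 give the same values as 0.3 and 0.2. More extreme splits lose more: 57.4% at 15:85 and 65.8% at 10:90.

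The base is one arm of about 50: 50 × 0.637 = 31.8, 50 × 0.576 = 28.8 and 50 × 0.490 = 24.5. So 50 children count as roughly 32 to 24.

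**Step 3. Sensitivity to the shape of the score.** The loss is one minus the squared correlation between the score and its split (simulation, 1,000,000 draws), over 20%, 50% and 80% below the cut.
- Uniform: 25% (50:50) to 52% (20:80).
- Exponential: 35% to 80%.
- Lognormal (log-scale SD of 1): 52% to 90%.

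**Step 4. What this could mean for power in one arm.** Assume n = 50, two-sided 0.05, a normal score and a true correlation r = 0.4 (not from the protocol). Power is approximately Φ(atanh(r)·√47 − 1.96), where a split replaces r by r·√(fraction kept).
- Continuous score: r = 0.400, power 83%.
- 50:50 split: r = 0.319, power 62%.
- 20:80 split: r = 0.280, power 51%.

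**Step 5. Does the predictor analysis already cover this?** Only in part. Sections 2.9 and 2.16 keep language and age continuous, but a factor enters the joint model only if it is significant on its own. Age adjustment of the language effect is therefore conditional, and nothing says that this model informs the comparison in 2.18.

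**The case against.** The strongest reply is that the protocol does not depend on the cut. Baseline word inventory and age are planned as continuous predictors, and baseline language level also appears in section 2.9 among subgroup and predictor factors with no cut attached. A reader might infer that the split is the only planned look at language, or that the trial discards the information altogether. The documents do not support either reading. What remains is that the comparison fixed in 2.18 still uses the cut without age, and that age adjustment elsewhere is not assured.

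A reader might also take 36-51% as a property of this trial. It is not. It needs a near-normal score, a linear relation and 20-80% of children below the cut, and none of these is stated. A uniform score split at its median would lose 25%, while skewed scores could lose much more. Nor should the loss be applied to all 100 children, since the comparisons are made within arms of about 50.

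The cut may be intended: the team may care about functional level at program entry rather than delay relative to age. That is a reasonable question and a reason to keep the threshold on display. It does not remove the possibility that age explains the difference.

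The example of an age-appropriate child just below the cut depends on the 12-month lower age limit. If 18 months applies, no such child is enrolled, though the mixing persists.

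Finally, functional form and covariates are often left to an analysis plan. Here, however, the protocol itself fixes the form of the comparison.

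**Conclusion.** The point stands as a minor one. The mixing of age with delay follows from the stated cut and the stated age range, and holds under either age range: 100% to 29% of age, or 67% to 29%. The loss of information is real in kind, but its size in this trial is unknown; about a third to a half is an illustration under the assumptions set out above.

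A reader might infer that section 2.18 tests whether language level changes the benefit of treatment. It does not. It compares outcomes between language groups within each arm, and a difference seen in one arm but not the other is no test of differential benefit.

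Section 2.18 presents these analyses as exploring effects, and the primary comparison of vocal responsiveness does not use the cut. No main conclusion of the trial is threatened.

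**What to change.** Reword section 2.18(3) to do the following.
- Use the baseline CDI score as a continuous variable, on a log scale or with a spline if it is skewed.
- Include child age in that model always, not subject to univariate significance.
- If the aim is to learn whether language level changes benefit, fit one model across both arms with an arm-by-CDI term, and show predicted outcomes by arm at a few CDI values.
- Keep the 12-month cut as a descriptive display, which preserves any clinical interest in that threshold.

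The two age ranges in sections 1.2 and 2.5 should also be reconciled, since they determine how wide the age mixing is.

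The cost is a few sentences and a simple change of model, and no new data are needed. The downside is an assumed shape for the relation between score and outcome, which a spline relaxes. An arm-by-CDI term will still be imprecise with about 50 children per arm, so the result should remain labelled exploratory.

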2.19 Has any pilot study been carried out using this design?

We have made *two substantive adaptations to the standard Social ABCs program*, each with some pilot data. First, we developed a **Group-based** protocol for didactic learning and shortened the duration of 1:1 coaching (6 vs. 12 weeks). We have pilot tested the Group adaptation ($n = 45$ in-person families) with positive reports from families and Coaches (see *Report to Alva Foundation*, attached). Preliminary analyses⁴³ reveal significant gains in toddler responsiveness and parent fidelity comparable to those for the original model (see Fig. 1 and 2). Unique to the Group model is evidence of **reduced parenting stress** (Fig 3), which highlights the enhanced clinical impact of a Group-based intervention that goes beyond increased efficiency²⁸. Parents in the Group model also reported improved toddler language (words understood and spoken³⁸ significantly increased, p 's $< .001$), reduced toddler autism symptoms (APSI³⁷ scores decreased significantly from 20.5 to 17.2; $p = .0005$), and high satisfaction (33.1 out of a possible 35).

The second key adaptation to our original model involved developing a **virtual coaching protocol** for the Group model. Our team made this additional adaptation in April 2020, in response to the Covid-19 pandemic, *and we have already piloted this adapted virtual Group model with an additional 22 families (and 11 in progress)*, demonstrating the feasibility and promise of this novel approach. Preliminary analyses of the **virtual Group-based adaptation** reveal outcomes similar to the *in-person Group model*, with comparable gains in parent fidelity (from 30.8% to 72.2%; $p = .009$) and a trend toward reduced parenting stress (from 31.8 to 25.5) similar in magnitude to the in-person values. Although child-level video data have not yet been coded, parent-reported autism symptoms (on the APSI³⁷) decreased significantly (23.2 to 18.5; $p = .004$), and satisfaction was high (32.5 out of 35). Parent-reported toddler language also increased (p 's = .003, .018, respectively for words understood and spoken). ***On all metrics evaluated to date, changes are commensurate across in-person and virtual delivery methods.***

The **adapted, virtual group delivery model** is a promising, innovative and cost-efficient way to provide intervention to toddlers with probable or confirmed autism at the first signs of concern.

3. Trial Management

3.1 What are the arrangements for day to day management of the trial?

The team already has procedures in place to facilitate trial management; we have access to a senior Research Coordinator (RC), experienced in clinical trials management on multi-site intervention trials. She will oversee registration of the trial with clinicaltrials.gov and management of cross-site collaboration to ensure consistency and compliance. The central RC will assign randomization codes and ensure blinding of videos in preparation for coding. We have a full complement of trained Coaches and Research Assistants at each site. Because the project is **entirely virtual**, we do not anticipate any study delays or stoppages related to current or future Covid-19 measures.

The ***steering committee*** will consist of [name], [name], [name], two senior Coaches ([name] and [name]), and one family advisor, and will meet formally every six months throughout the project, with ad hoc meetings as needed. Statistical analyses will be conducted by [name] and [name], with consulting support through the University of Toronto (OISE) statistical support service. Despite low anticipated risk, we will establish a ***data safety and monitoring board*** using processes in place in our current work, with members external to the conduct of the study: one scientist, one member with biostatistics expertise, and one family advisor (different from those named above). This committee will meet twice yearly to review enrollment, completion, and withdrawal rates, adherence to the study protocol, protocol violations or deviations, any adverse events (which are also reported to our Research Ethics Boards), and external factors that might affect the ethics of the study.

References

2. American Psychiatric Association. *Diagnostic and statistical manual of mental disorders, Fifth Edition* (DSM-5). 2013. Washington, DC: American Psychiatric Association.
